7.4.2 Safety

AEs and SAEs will be tabulated by preferred term using the Medical Dictionary for Regulatory Activities (MedDRA), by System Organ Class (SOC) and by severity. The subset of AEs that are assessed by the Investigator as having a relationship to the IP will be considered to be treatment-related AEs. The number and percentage of AEs and treatment-related AEs will be tabulated by treatment arm and overall. AEs will also be summarized by severity, relatedness and seriousness. AEs will be analyzed both by ITT and by treatment received, in the Safety Population. Comparisons of rates of AEs will be presented descriptively.

7.5 Analysis for Exploratory Outcomes

7.5.1 Efficacy

Responses to ePROs (WHODAS 2.0 36-item score, PROMIS Fatigue 7a, Insomnia Severity Index, PROMIS Cognitive Function Short Form 6A, DSQ-PEM Short Form,

Headache Diary, COMPASS 31) will be tabulated and change in response between baseline and each study visit (6, 9, 12 weeks) will be calculated. Comparisons of changes in responses will be made between subjects receiving study drug versus placebo.

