Secondary Objectives: Secondary objectives are to assess completion rate of quality of life assessments, adherence to Investigational Product, attrition rates and safety.

Exploratory Objective: The exploratory objective is to assess efficacy of histamine receptor antagonist (HRA) therapy in improving outcomes in patients with Post-Acute Sequelae of Coronavirus-19 (PASC) and at least one of the following symptoms: fatigue, post-exertional malaise (PEM), headache, brain fog, sleep disturbance, dysautonomia.

3. Background

In December 2019, a new human coronavirus with respiratory tropism, SARS-CoV-2, emerged in China and rapidly spread to other parts of the world [6, 7]. The coronavirus disease 2019 (COVID-19) has resulted in over 100 million confirmed cases of infection [8]. Although there are numerous publications describing the wide range of acute phase manifestations, there remains limited data on long-term sequelae of COVID-19, aka Post-Acute Sequelae of SARS-CoV-2 (PASC) or “Long COVID”. PASC may occur in 20-30% of COVID-19 patients, and symptoms result in significant impairments in quality of life [9-18]. With the growing prevalence of COVID-19, PASC is creating a substantial global burden [19]. Though common complaints include dyspnea, fatigue, brain fog, weakness, pain syndromes, anxiety, and depression, PASC can manifest as a myriad of symptoms [10, 11, 13]. In many, these symptoms can persist for >6 months, and the true duration of this disease remains unclear [13].

Though the underlying pathophysiology of PASC symptoms remains unknown, several mechanisms have been proposed in individuals with no detectable parenchymal or structural damage resulting from acute COVID-19 infection. SARS-CoV-2 can persist in bodily

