6.1 Study Design

This is a fully decentralized, single center, randomized, double-blind, placebo controlled, clinical trial to evaluate the safety, tolerability, and feasibility of a potential treatment for PASC.

Upon confirmation of eligibility, the investigational pharmacist will randomize subjects 2:1 treatment versus placebo. Treatment consists of 10mg of cetirizine daily and 20mg of famotidine twice daily. Placebos will match the morphology of the treatments but contain no active ingredients. Study subject and study team will be blind to assigned treatment; only the IDS will be unblind.

Subjects will be followed for safety, tolerability, and responses to patient reported outcome (PROs) over 12 weeks. At Week 12, End of Study, subjects will be required to complete a questionnaire that addresses several aspects of feasibility of participating in the study.

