6.5 Detailed Study Procedures and Assessments by Study Period/Study Day

The procedures performed during this study will be performed according to this section and the Schedule of Events table shown in Section 6.7 below.

6.5.1 Screening (Within 28 days ± 3 days of Day 0):

Prior to any study-specific procedures or data collection, the CRC will obtain informed consent from potentially eligible subjects. If the subject is not an Emory patient, the subject will be asked to sign a medical release form. Using a verbal consent, subjects will be prescreened by televisit by the CRC who will review the inclusion/exclusion criteria. Subjects who remain interested and are potentially eligible will then be consented, and medical records will be sought from the subject's healthcare system to confirm eligibility.

The following procedures and data collection will be performed during Screening:

- Signature of electronic Informed Consent Form and provision of subject information

- Collection of sociodemographic data
- Medical record review
- Collection of medical and surgical history, including acute COVID-19 history, PASC history (time from symptom onset or positive SARS-CoV-2 testing), and COVID-19 vaccination status
- Assessment routine concomitant medications
- Assessment of baseline PROs:
 - WHODAS 2.0 36-item score
 - PROMIS Fatigue 7a
 - Insomnia Severity Index
 - PROMIS Cognitive Function Short Form 6A
 - DSQ-PEM Short Form
 - Headache Diary (completed daily during the 7 days prior to visit)
 - COMPASS 31
- Confirm Inclusion and Exclusion criteria

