7.2 Population for Analysis

The following populations will be used in the analyses:

- Intent-to-treat (ITT): All subjects who received at least one intake of IP. Subjects will be analyzed according to their assigned treatment.

- Per protocol (PP): All subjects in the ITT population who were free from major protocol violations that could lead to bias
- Safety: All subjects who received at least one intake of IP. Subjects will be analyzed according to the treatment they actually received.

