Incidental findings are not anticipated in this study because there are no investigational diagnostic tests. However, if we discover a medical issue that is unrelated to the purpose of this study, we will share that information if it is of urgent medical importance.

10. Study Timelines

- The duration of participation for each individual subject will be 16 weeks—4 weeks Screening, 12 weeks Treatment.
- Based on the current epidemiology, the duration of recruitment should be approximately four (4) months from first subject enrolled.
- Last subject last visit is anticipated to occur in August 2024. The estimated date for the investigators to complete primary analyses is February 2025.

11. Inclusion and Exclusion Criteria

- CRC will pre-screen Emory and Grady PASC Clinic patients for potential eligibility via chart review and will contact the clinic physician regarding potentially eligible patients. CRC will request clinic physician advise patients of the study and provide CRC/study team contact information to interested patients. CRC/study team will describe the study to these potential subjects and will send the ICF to interested patients for the ICF discussion.
- Non-Emory subjects will contact CRC/study team in response to recruitment advertisements. CRC/study team will confirm the potential subject is 18 years of age or older and a Georgia resident with new or worsened symptoms of interest since onset of COVID-19 that have lasted for \geq 12 weeks. CRC/study team will describe the study to

these potential subjects and will send the ICF to interested subjects to conduct the ICF discussion.

- Potential subjects will not complete baseline questionnaires and CRC/study team will not conduct a full medical/surgical history and concomitant medication review for inclusion/exclusion prior to the subject signing the ICF.

Inclusion Criteria: A subject must meet all of the following criteria to be eligible for this study:

1. Adults ≥18 years of age with history of a SARS-CoV-2 PCR positive test and/or medical records from healthcare provider that coincides with the diagnosis of long-COVID
2. New or worsened symptoms since onset of COVID-19 that are persistent at the time of enrollment and have lasted for ≥ 12 weeks (including at least one of the following: fatigue, post-exertional malaise (PEM), headache, brain fog, sleep disturbance, dysautonomia).
3. Confirmation of negative urine or serum HCG (pregnancy) test in women of child-bearing potential

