24 subjects are needed to complete the research procedures. We anticipate enrolling and screening approximately 36 subjects to reach this goal, given screen failure and possible study drop-out/withdrawal. Screen failures will be replaced; drop-out/withdrawal/lost to follow-up will not be replaced. Participants will be drawn from the state of GA. We project enrollment to reflect the incidence of PASC between the sexes of 70% female and 30% male. PASC incidence among races is unknown.

15. Recruitment Methods

Recruitment will be done through a two-pronged approach utilizing direct engagement with Long COVID clinics at Grady and Emory.

We will engage with clinicians at PASC and primary care clinics at Emory and Grady. Promotion will entail a combination of direct outreach and education from our team along with materials such as flyers and pamphlets.

The study team will review medical records for Emory and Grady PASC Clinic patients to identify potentially eligible prospective subjects, per protocol Section 11 Inclusion and Exclusion Criteria.

Finally, we will share our graphics with Emory's communications team and request placement on their website and dissemination of information about the trial.

16. Withdrawal of Participants

Participants may discontinue IP or withdraw from the study at any time and for any reason without prejudice to their medical care. Furthermore, the PI may discontinue a subject from IP or withdraw them from study procedures. The reason for the patient's discontinuation or withdrawal will be recorded in REDCap.

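### Section 7.5.1 does not say whether the between-arm comparison of PRO changes adjusts for the baseline score; ANCOVA on baselines already collected would usually be more precise at almost no cost.

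*Combined protocol and SAP*

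**What the plan says.** Section 2 sets efficacy as the exploratory objective: "The exploratory objective is to assess efficacy of histamine receptor antagonist (HRA) therapy". Section 7.5.1 holds the only between-arm efficacy analysis. For seven PROs, "change in response between baseline and each study visit (6, 9, 12 weeks) will be calculated", and then "Comparisons of changes in responses will be made between subjects receiving study drug versus placebo". No model, test, covariate or interval is named.

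No other section fills the gap. The only statement about covariates, in section 12, rules out race and ethnicity and is silent on baseline scores. References 3 to 5 in section 27 include works on longitudinal analysis and covariate adjustment, but section 7 does not cite them.

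The baselines are available. Section 6.5.1 lists "Assessment of baseline PROs" among the Screening procedures, with the same seven instruments that section 6.5.6 repeats at Days 42, 63 and 84.

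On size, section 6.1 states that "the investigational pharmacist will randomize subjects 2:1 treatment versus placebo", and section 14 that "24 subjects are needed to complete the research procedures", out of about 36 enrolled and screened.

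**The concern.** Carried out literally, with no covariate, section 7.5.1 gives a difference in mean change. That estimator fixes the coefficient on baseline at 1 instead of estimating it. This has two consequences in a trial of about 16 versus 8:

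- Chance baseline differences are common at this size, and the change score over-corrects for them whenever the true slope is below 1.
- The estimate is usually noisier than one from a model that includes baseline.

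What is at stake is the precision of the trial's only treatment comparison on the PROs. The feasibility endpoints are tabulated separately and are not touched.

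**Working it through.** The plan states no power, SD, effect size or precision target, so there is no figure of its own to reproduce. The check compares the two estimators at the trial's size.

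**Inputs from the documents.** 24 completers (section 14) at 2:1 (section 6.1) gives 16:8. The 36 in section 14 includes screen failures, so 24:12 is an upper bound.

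**Assumed inputs.** The baseline/follow-up correlation ρ is not given; 0.3 to 0.9 is used. SDs are first taken as equal at baseline and follow-up, with a common linear slope. Results are in SD units.

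**Formulas**, with s = √(1/n₁ + 1/n₂):

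- Change score: half-width = t(N−2) × √(2(1−ρ)) × s
- ANCOVA: half-width = t(N−3) × √((1−ρ²)(1 + 1/(N−4))) × s
- Variance ratio, ANCOVA/change = ((1+ρ)/2) × (1 + 1/(N−4))

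The factor 1 + 1/(N−4) is the small-sample cost of estimating the slope.

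**At 16:8:** s = √(1/16 + 1/8) = 0.433; the factor is 1 + 1/20 = 1.05; t(22) = 2.074 and t(21) = 2.080. For ρ = 0.5:

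- Change: 2.074 × √1.0 × 0.433 = 0.898
- ANCOVA: 2.080 × √(0.75 × 1.05) × 0.433 = 0.799
- Variance ratio: 0.75 × 1.05 = 0.788

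| ρ | Change, 16:8 | ANCOVA, 16:8 | Variance ratio, 16:8 | Change, 24:12 | ANCOVA, 24:12 |
|---|---|---|---|---|---|
| 0.3 | 1.063 | 0.880 | 0.683 | 0.850 | 0.697 |
| 0.5 | 0.898 | 0.799 | 0.788 | 0.719 | 0.633 |
| 0.7 | 0.696 | 0.659 | 0.892 | 0.557 | 0.522 |
| 0.8 | 0.568 | 0.554 | 0.945 | 0.454 | 0.438 |
| 0.9 | 0.402 | 0.402 | 0.997 | 0.321 | 0.318 |

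On variance, the methods break even at ρ = 2/1.05 − 1 = 0.905 for 16:8, and at 2/1.031 − 1 = 0.939 for 24:12. Simulation at 16:8 (20,000 trials per setting) gave variance ratios of 0.68, 0.79, 0.89 and 1.00 at ρ = 0.3, 0.5, 0.7 and 0.9. For an assumed true difference of 0.8 SD at ρ = 0.5, simulated power was 0.42 unadjusted and 0.51 adjusted, with type I error near 0.05 for both.

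**Chance baseline difference.** The difference d in baseline means has standard error 0.433 SD, so P(|d| > 0.5 SD) = P(|Z| > 0.5/0.433) = 0.248 at 16:8. At 24:12 it is 0.157. Given d, the change contrast is off by (ρ−1)d. At d = 0.5 that is −0.35, −0.25, −0.15, −0.10 and −0.05 SD for ρ = 0.3, 0.5, 0.7, 0.8 and 0.9.

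**Unequal SDs.** With k = follow-up SD / baseline SD, the 16:8 variance ratio is k²(1−ρ²) × 1.05 / (1 + k² − 2ρk).

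| k | ρ = 0.5 | ρ = 0.7 | ρ = 0.9 |
|---|---|---|---|
| 0.8 | 0.600 | 0.659 | 0.638 |
| 1.25 | 0.938 | 1.030 | 0.997 |

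**Floor effects.** Section 11 requires only one symptom from a list ("including at least one of the following: fatigue, post-exertional malaise (PEM), headache, brain fog, sleep disturbance, dysautonomia"), so some subjects may sit at the floor of scales for symptoms they do not have. Normal scores were simulated at 16:8 and cut at a floor, with no treatment effect. At latent correlations 0.5, 0.7 and 0.9 the variance ratios were 0.766, 0.863 and 0.979 with 30% at the floor, and 0.719, 0.839 and 0.953 with 50%. ANCOVA coverage was 94.9% to 95.6%, and its mean error was within 0.003 SD of zero. These are correlations before the cut, so the ratios are not directly comparable with the first table.

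**The case against.** The strongest reply is that the plan has made no mistake. The text is silent on baseline; it does not reject it. Regressing change on arm and baseline gives the same treatment estimate as ANCOVA on the follow-up score, so a comparison of changes can already be an adjusted one. Efficacy is exploratory in a pilot with no precision target, and a short descriptive plan is defensible. **This stands**, and it limits the point to an optional improvement. It does not remove it, because a literal reading would produce the unadjusted contrast.

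The gain also rests on assumed values of ρ and the SD ratio. **This stands too.** At ρ of 0.7 to 0.8 with equal SDs the half-width narrows by only 0.01 to 0.04 SD. With k = 1.25 there is almost no gain, and a small loss at ρ = 0.7. With unequal SDs the imbalance factor becomes kρ − 1, which is zero at k = 1.25 and ρ = 0.8. However, the largest loss in the cases examined is about 3% in variance, against reductions of 21% at ρ = 0.5 and 32% at ρ = 0.3 with equal SDs.

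Separate ANCOVAs per visit are one choice among several; a single repeated-measures model with baseline as covariate would also be reasonable. Finally, the plan defines no summary score for the Headache Diary. That is true, but it leaves the plan's own change score equally undefined.

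**Conclusion.** The point holds as a free improvement. Section 7.5.1 leaves baseline adjustment unstated, and adjustment would usually sharpen the efficacy estimate using data already in hand. At 16:8 with equal SDs, variance falls by about 32%, 21% and 11% at ρ = 0.3, 0.5 and 0.7, and not at all from about 0.9. Adjustment also removes the part of a chance baseline difference that the change score carries, under a linear model with a common slope.

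The size depends on a correlation and an SD ratio that the documents do not give. With either method the interval stays wide: for ρ from 0.3 to 0.7, the adjusted half-width is still 0.88 to 0.66 SD. No stated decision depends on this analysis.

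**What to change.** Add to section 7.5.1: *For each PRO, the treatment difference at Weeks 6, 9 and 12 will be estimated by ANCOVA with the baseline score of that PRO as covariate, and reported with its 95% CI as an exploratory estimate without multiplicity adjustment; change scores will also be tabulated.*

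The exploratory label matters. There are 7 × 3 = 21 contrasts, so with no true effect about 21 × 0.05 = 1.05 intervals would be expected to exclude zero by chance.

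For scales likely to be strongly skewed or near their floor, the Headache Diary in particular, say that the linear model will be checked. Define the Headache Diary summary score, and name any alternative analysis before unblinding so that the choice does not follow the results. As a separate clarification, the same edit can name the ITT population, for which section 7.2 says "Subjects will be analyzed according to their assigned treatment".

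The cost is one or two sentences, slightly more analysis work and one degree of freedom per model. No data, visits or subjects are added: a change score already needs both values, so the same subjects contribute.

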7.5 Subject Disposition

The disposition of all subjects in the various populations will be summarized by treatment arm as follows:

- Number of subjects randomized
- Number of subjects who completed the study
- Number of subjects who discontinued IP
- Number of subjects who withdrew from the study
- Number of subjects lost to follow-up

All subjects who discontinued the study will be listed by treatment arm with the reason for discontinuation, if available

8. Data and/or Specimen Banking

Data will be shared among members of the study team with appropriate access based on study role, training, and delegation of authority. Data will be made available to assigned study monitors, the appropriate oversight authorities, the Food and Drug Administration, and other state and federal regulatory authorities as required by state and federal law.

De-identified data may be shared for future research. Requests will be evaluated on a case-by-case basis by PI. No data will be released without proof of IRB approval or determination. Agreements as required by local policies will be completed when necessary, including data use agreements and material transfer agreements.

The study will be registered with one or more recognized clinical study registries, e.g., www.clinicaltrials.gov.

All data and results and all intellectual property rights in the data and results derived from the study will be the property of the Sponsor who may utilize them in various ways, such as for submission to regulatory authorities or shared with research institutions, as needed.

The final Clinical Study Report will be submitted to the ethics committee and regulatory authorities, if required.

The Sponsor encourages the communication and/or publication of the results by the consortium of partners in accordance with the terms of the Clinical Trial Agreement.

Subjects will have the option of consenting to be contacted for future related studies. If subjects choose this option, their name and contact information will be stored in a password-protected file stored on a secure, Emory server.

9. Sharing of Results with Participants

Individual subject results will not be shared with participants. Participants interested in knowing their randomization assignment may request that staff release that information after unblinding occurs after database lock. Participants desiring study results may request that staff provide them links to any publications resulting from the trial.

Incidental findings are not anticipated in this study because there are no investigational diagnostic tests. However, if we discover a medical issue that is unrelated to the purpose of this study, we will share that information if it is of urgent medical importance.

10. Study Timelines

- The duration of participation for each individual subject will be 16 weeks—4 weeks Screening, 12 weeks Treatment.
- Based on the current epidemiology, the duration of recruitment should be approximately four (4) months from first subject enrolled.
- Last subject last visit is anticipated to occur in August 2024. The estimated date for the investigators to complete primary analyses is February 2025.

11. Inclusion and Exclusion Criteria

- CRC will pre-screen Emory and Grady PASC Clinic patients for potential eligibility via chart review and will contact the clinic physician regarding potentially eligible patients. CRC will request clinic physician advise patients of the study and provide CRC/study team contact information to interested patients. CRC/study team will describe the study to these potential subjects and will send the ICF to interested patients for the ICF discussion.
- Non-Emory subjects will contact CRC/study team in response to recruitment advertisements. CRC/study team will confirm the potential subject is 18 years of age or older and a Georgia resident with new or worsened symptoms of interest since onset of COVID-19 that have lasted for \geq 12 weeks. CRC/study team will describe the study to

these potential subjects and will send the ICF to interested subjects to conduct the ICF discussion.

- Potential subjects will not complete baseline questionnaires and CRC/study team will not conduct a full medical/surgical history and concomitant medication review for inclusion/exclusion prior to the subject signing the ICF.

Inclusion Criteria: A subject must meet all of the following criteria to be eligible for this study:

1. Adults ≥18 years of age with history of a SARS-CoV-2 PCR positive test and/or medical records from healthcare provider that coincides with the diagnosis of long-COVID
2. New or worsened symptoms since onset of COVID-19 that are persistent at the time of enrollment and have lasted for ≥ 12 weeks (including at least one of the following: fatigue, post-exertional malaise (PEM), headache, brain fog, sleep disturbance, dysautonomia).
3. Confirmation of negative urine or serum HCG (pregnancy) test in women of child-bearing potential
4. Willing to use appropriate contraceptive for female and male subjects for the duration of the study
5. Has an address (for mailing of IP) in the state of Georgia
6. Able to swallow capsules
7. Has reliable access to a mobile phone, tablet, laptop, or desktop computer capable of connecting to the internet via WiFi or a data plan
8. Available lab work (CBC and CMP) after onset of long COVID symptoms
9. Willing and able to comply with scheduled visits, treatment plan, and other study procedures including receiving either intervention or placebo
10. Willing to not take any of the study medications while enrolled in the study except for essential need as prescribed by a healthcare provider

Exclusion Criteria: A subject who meets any of the following criteria will be excluded from this study:

1. No PASC symptoms at the time of enrollment or PASC symptoms present <12 weeks at the time of enrollment
2. Inability to provide own informed consent
3. Currently hospitalized

4. For Women of Child Bearing Potential (WOCBP)*: currently pregnant or plans to become pregnant during study period; for males with partners OCBP, plans to become pregnant during study period
5. Actively enrolled in another Long COVID/PASC interventional trial or participation in another interventional clinical trial in the last 30 days or planned during the trial period
6. Unstable medical comorbidities (e.g., decompensated cirrhosis, stage III-IV chronic kidney disease, NYHA class III congestive heart failure), per subject report, telemedicine physical exam, baseline laboratory values (hematology and extended chemistry panels) and/or medical records
7. Other medical conditions occurring either before or after onset of COVID-19 that can otherwise account for PASC-type symptoms (examples include, but are not limited to: uncontrolled thyroid disease, adrenal insufficiency, chronic fatigue syndrome, Postural Orthostatic Tachycardia Syndrome (POTS), among others). This will be up to the discretion of the study physician.
8. Currently immunocompromised from the following: solid organ transplant, BMT, high dose steroids (>20mg prednisone per day), immune modulators, or chemotherapy
9. Currently taking opioid analgesics, undergoing treatment for opioid addiction, or taking any other prohibited concomitant medication
10. Opioid dependence or withdrawal syndrome
11. Known sensitivity or adverse reaction to H1 or H2 receptor antagonists, or medication components
12. Suspected or confirmed pregnancy or breastfeeding
13. Already on H1 or H2 receptor antagonists within 3 months of randomization
14. Currently receiving other therapies to treat COVID-19 or Long COVID symptoms, e.g., convalescent plasma, remdesivir, Paxlovid

*WOCBP are defined as a person of childbearing ability who has not had a hysterectomy and/or both tubes and/or both ovaries removed and/or is not postmenopausal and over the age of 45).

12. Population

The study population will consist of Georgia residents ages ≥ 18 years with new or worsened symptoms since the onset of COVID-19 that are persistent at the time of enrollment and have lasted for ≥ 12 weeks. Subjects must have at least one of the following PASC symptoms: fatigue, post-exertional malaise (PEM), headache, brain fog, sleep disturbance, or dysautonomia.

The following special populations will not be enrolled in this study:

- Adults unable to consent

- Individuals who are not yet adults (infants, children, teenagers)
- Pregnant women
- Prisoners
- Cognitively impaired or Individuals with Impaired Decision-Making Capacity
- Individuals who are not able to clearly understand English

This study will use the 2020 US Census classifications for race and ethnicity data as established in the 1997 Office of Management and Budget (OMB) Standards and described at:

<https://www.govinfo.gov/content/pkg/FR-1997-10-30/pdf/97-28653.pdf>. Race categories will include American Indian or Alaska Native, Asian, Black or African American, Native Hawaiian or Other Pacific Islander, White and Some Other Race. More than one race may be selected. Ethnicity will ask if subjects are or are not of Hispanic, Latino/a/x or Spanish origin. Both race and ethnicity will include a write-in section in which participants can self-identify.

Racial and ethnic classifications of subjects will be used for descriptive statistics, but will not be used within an explanatory model (as a covariate).

13. Vulnerable Populations

This trial will not enroll subjects who are members of vulnerable populations.

14. Local Number of Participants

24 subjects are needed to complete the research procedures. We anticipate enrolling and screening approximately 36 subjects to reach this goal, given screen failure and possible study drop-out/withdrawal. Screen failures will be replaced; drop-out/withdrawal/lost to follow-up will not be replaced. Participants will be drawn from the state of GA. We project enrollment to reflect the incidence of PASC between the sexes of 70% female and 30% male. PASC incidence among races is unknown.

15. Recruitment Methods

Recruitment will be done through a two-pronged approach utilizing direct engagement with Long COVID clinics at Grady and Emory.

We will engage with clinicians at PASC and primary care clinics at Emory and Grady. Promotion will entail a combination of direct outreach and education from our team along with materials such as flyers and pamphlets.

The study team will review medical records for Emory and Grady PASC Clinic patients to identify potentially eligible prospective subjects, per protocol Section 11 Inclusion and Exclusion Criteria.

Finally, we will share our graphics with Emory's communications team and request placement on their website and dissemination of information about the trial.

16. Withdrawal of Participants

Participants may discontinue IP or withdraw from the study at any time and for any reason without prejudice to their medical care. Furthermore, the PI may discontinue a subject from IP or withdraw them from study procedures. The reason for the patient's discontinuation or withdrawal will be recorded in REDCap.

